#### 7.4.4 Additional Endpoints

No formal statistical hypothesis will be formulated and performed for the additional endpoints. Additional details are described in section 7.11 in the SAP.

##### 7.4.4.1 Additional Procedural Endpoints

- Total procedure time, PVI time, PF/RF application time and mapping time
- Number of PF/RF applications
- Total fluoroscopy time
- Total study catheter left atrial dwell time
- Ablation settings used
- Use of paralytics and type of anesthesia

##### 7.4.4.2 Additional Safety Endpoints

Additional safety endpoints, including SADEs, UADEs and USADEs, SAEs, and non-SAEs:

- Incidence of Serious Adverse Device Effects (SADEs)
- Incidence of Unanticipated (Serious) Adverse Device Effects (UADEs and USADEs)
- Incidence of Serious Adverse Events (SAEs) within 7 days (early-onset), 8-30 days (peri-procedural), and >30 days (late onset) of initial ablation procedure, separately for each timeframe
- Incidence of non-serious adverse events (non-SAEs)

##### 7.4.4.3 Additional Effectiveness Endpoints

- **Single Procedural Success:** defined as freedom from documented symptomatic atrial arrhythmia (AF, AT or AFL of unknown origin\*) episodes based on electrocardiographic data ( $\geq 30$  seconds on arrhythmia monitoring device) during the effectiveness evaluation period (Day 91-Day 365) following a single index ablation procedure. Subjects who had repeat procedure(s) for the study arrhythmia post the index procedure will be deemed failures of this endpoint.
- **Freedom from documented symptomatic atrial arrhythmia (AF, AT or AFL of unknown origin\*):** defined as freedom from the documented symptomatic atrial arrhythmia (AF, AT or AFL of unknown origin\*) recurrence

based on electrocardiographic data ( $\geq 30$  seconds on arrhythmia monitoring device) during the effectiveness evaluation period (Day 91-Day 365).

Acute procedural failure (i.e., failure to confirm entrance block in all PVs except those that are silent and/or cannot be cannulated post-procedure, use of non-study catheter for PV isolation, and failure to have energy delivery with the study device due to ablation system malfunctions) will also be considered a failure.

- **Freedom from documented (symptomatic and asymptomatic) atrial arrhythmia (AF, AT or AFL of unknown origin\*) with additional failure modes:** defined as freedom from documented (symptomatic and asymptomatic) atrial arrhythmia (AF, AT or AFL of unknown origin\*) based on electrocardiographic data ( $\geq 30$  seconds on arrhythmia monitoring device) during the effectiveness evaluation period (Day 91-Day 365). The following criteria will also be deemed failures:
  - Failure to achieve acute procedural success.
  - Taking a new Antiarrhythmic Drug (AAD) (Class I / Class III) for atrial tachyarrhythmia (AF, AT or AFL of unknown origin\*) or taking a previously failed Class I/III AAD at a greater than the highest ineffective historical dose for AF/AFL/AT during the effectiveness evaluation period (Day of 3-month visit\* – Day 365).
  - Greater than 1 repeat ablation for AF/AT or AFL of unknown origin\* in the blanking period or any repeat ablation for AF/AT or AFL of unknown origin\* during the effectiveness evaluation period.

*\*Note: The upper bound of the 3-month visit will be considered as the start point of the evaluation period of AAD failure, which is Day 105. As it is a common practice for medications to be adjusted and/or stopped during an in-clinic visit (i.e., 3-month follow-up visit), subject may have his/her medication adjusted or stopped during the CIP-defined follow-up window, including the Class I/III AADs.*

- **Use of a non-study device** for the purpose of PVI (i.e., touch-up) and/or for the ablation of left atrial non-PV AF targets (i.e., posterior wall) during index ablation procedure or within-lanking repeat procedures.
- **Acute reconnection:** any reconnection in the PVs that are identified after adenosine/isoproterenol challenge among all targeted PVs.

- **Repeat ablation procedures** for left atrial arrhythmia (AF, AT or AFL of unknown origin\*) within the 12-month FU period. Procedures for CTI dependent flutter in the follow-up period are not considered repeat procedures per CIP.
- **Quality of Life (QoL):** defined as the change of QoL which is assessed by comparing the Atrial Fibrillation Effect on Quality-of-Life (AFEQT™) scores before and at 3, 6 and 12- months after the ablation procedure.
- **Hospitalization for cardiovascular events** through 12-month follow-up compared to 12 months prior to baseline.

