7.3.3 Additional Effectiveness Endpoints

PVI Durability Rate

- Percentage of targeted PVs in the index ablation procedure being durably isolated as confirmed by the electroanatomical mapping 75 days (+/- 15days) post index ablation procedure.
- Percentage of subjects with durably isolated targeted PVs as confirmed by the electroanatomical mapping at 75 days (+/- 15days) post index ablation procedure.

Single Procedural Success: defined as freedom from documented symptomatic atrial arrhythmia (AF, AT or AFL of unknown origin*) episodes based on electrocardiographic data (≥ 30 seconds on arrhythmia monitoring device) during the effectiveness evaluation period (Day 91-Day 365) following a single index ablation procedure.

Freedom from documented symptomatic atrial arrhythmia (AF, AT or AFL of unknown origin *) episodes based on electrocardiographic data (≥ 30 seconds on arrhythmia monitoring device) during the effectiveness evaluation period (Day 91-Day 365). Acute procedural failure will also be considered failure of 12-month symptomatic recurrence free endpoint.

Freedom from documented (symptomatic and asymptomatic) atrial arrhythmia (AF, AT or AFL of unknown origin*) episodes based on electrocardiographic data (≥ 30 seconds on arrhythmia monitoring device) during the effectiveness evaluation period (Day 91-Day 365) with extra failure modes. A subject who meets any of the following criteria will also be deemed an effectiveness failure:

- Failure to achieve acute procedural success.
- Taking a new Antiarrhythmic Drug (AAD) (Class I / Class III) for atrial tachyarrhythmia (AF, AT or AFL of unknown origin*) or taking a previously failed Class I/III AAD at a greater than the highest ineffective historical dose for AF/AFL/AT during the effectiveness evaluation period (Day of 3-month visit – Day 365).
- Greater than 1 repeat ablation for AF/AT or AFL of unknown origin* in the blanking period or any repeat ablation for AF/AT or AFL of unknown origin* during the effectiveness evaluation period.

Use of a non-study device for the purpose of:

- PVI (i.e., touch-up) among all clinically relevant targeted PVs and by subject
- Ablation of left atrial non-PV AF targets (i.e., posterior wall) during index ablation procedure or for repeat procedures during blanking period.

Acute reconnection identified by adenosine/isoproterenol challenge among all clinically relevant targeted PVs

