### 7.1.3 Handelling Subjects with Specific Ablation Scenarios in Effectiveness Endpoint Analysis

Subjects who undergo ablation using the investigational ablation system or commercial ablation devices at the **PV/CTI regions or outside the PV/CTI regions** will be included in the analysis of acute and long-term effectiveness endpoints according to the following guidelines:

- Condition 1: Subjects who undergo ablation **using the investigational ablation system for PV isolation** will be included in the analysis of acute effectiveness endpoints.
  - If the PV isolation is completed using commercial RF (radiofrequency) devices due to reasons related to the study system (SMARTTOUCH™ SF (STSF) and TRUPULSE™ Generator), the subject will be considered a failure for the acute effectiveness endpoint and be included in acute and long-term effectiveness endpoint analyses..
  - If the PV isolation is completed using commercial RF devices due to reasons unrelated to the study system (SMARTTOUCH™ SF (STSF) and TRUPULSE™ Generator), the subject will be considered not evaluable for the effectiveness of the investigational system and will be excluded from the analyses of acute and long-term effectiveness endpoints.
- Condition 2: The use of the **investigational ablation system outside the PV/CTI region is not permitted** according to the protocol. Subjects who undergo ablation outside the intended regions using investigational ablation system will be excluded from the long-term effectiveness endpoint analysis, unless they have already failed the acute effectiveness endpoint. Subjects who failed the acute effectiveness endpoint will also be considered failures for the long-term effectiveness endpoint.

- Condition 3: In cases where **commercial RF devices are used for ablation outside the PV region and/or CTI line** to treat arrhythmia identified during the procedure, it is allowed for the well-being of the patient. However, these subjects will be excluded from the long-term effectiveness analysis, as they received additional ablations beyond the intended treatment using non-investigational devices. This exclusion is necessary to avoid mixed effects from non-study devices that could confound the interpretation of the long-term effectiveness results for the investigational devices.

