#### 7.4.3 Secondary Effectiveness Endpoint

The secondary effectiveness endpoint is freedom from documented (symptomatic and asymptomatic) atrial arrhythmia episodes including atrial fibrillation (AF), atrial tachycardia (AT), or atrial flutter (AFL) of unknown origin\* during the effectiveness evaluation period (Day 91-365). The AF/AT/AFL episodes will be identified based on electrocardiographic data.

Subjects with an AF/AT/AFL episode that is  $\geq 30$  seconds on arrhythmia monitoring device during the evaluation period device are considered failures of this long-term effectiveness endpoint. Acute procedural failure (i.e., failure to achieve entrance block with the study device in any of the targeted PVs) will also be deemed a failure of this endpoint.

To evaluate the secondary objective of the study, the 12-month effectiveness success rate will be compared against a PG of 50%. The formal hypotheses to test the secondary effectiveness endpoint is given as follows:

$$H_0: P_1 \leq 0.50 \quad \text{vs} \quad H_A: P_1 > 0.50$$

where  $P_1$  denotes the the proportion of subjects who are failure-free at 12-month follow-up.

\*AFL of unknown origin is defined as all AFL except those CTI dependent AFL as confirmed by 12-lead electrocardiogram (ECG) or entrainment maneuvers in an EP study.

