### **7.11.3 Additional Effectiveness Endpoints**

The additional effectiveness endpoints will be summarized descriptively in the PP and mITT analysis sets after all study subjects completed their 12-month follow up.

- **Single Procedural Success:** The number and percentage of subjects with single procedural success will be summarized. Kaplan-Meier estimates and plots will be used to characterize the time to first documented symptomatic atrial arrhythmia (AF, AT or AFL) recurrence following a single index ablation procedure.
- **Freedom from documented symptomatic atrial arrhythmia (AF, AT or AFL of unknown origin\*):** Kaplan-Meier estimates and plots will be used to characterize the time to first documented symptomatic atrial arrhythmia (AF, AT or AFL of unknown origin\*) recurrence based on electrocardiographic data ( $\geq 30$  seconds on arrhythmia monitoring device) during the effectiveness evaluation period (Day 91-Day 365).
- **Freedom from documented (symptomatic and asymptomatic) atrial arrhythmia (AF, AT or AFL of unknown origin\*) with additional failure modes:** Kaplan-Meier estimates and plots will be used to characterize the time to first documented (symptomatic and asymptomatic) atrial arrhythmia (AF, AT or AFL of unknown origin\*) based on electrocardiographic data ( $\geq 30$  seconds on arrhythmia monitoring device) during the effectiveness evaluation period (Day 91-Day 365).

The event-free rate will also be summarized descriptively as the number and percent of subjects free from documented (symptomatic and asymptomatic) atrial arrhythmia (AF, AT or AFL of unknown origin\*) during the evaluation period.

- **Use of a non-study device:**

- The number and percentage of subjects and number and percent of PVs ablated by a non-study catheter (NSC) for PVI will be summarized.

- Rate of ablation by NSC for PVI among all targeted pulmonary veins during index procedure:

$$= \frac{\text{Number of PVs ablated by NSC}}{\text{Number of ablated PVs}}$$

- Rate of ablation by NSC for PVI among subjects during index procedure:

$$= \frac{\text{Number of subjects with at least one PV ablated by NSC}}{\text{Total number of subjects ablated for PVI}}$$

- Ablation of left atrial non-PV AF targets (i.e., posterior wall) during index ablation procedure or for repeat procedures during the blanking period.

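### Single Procedural Success has no acute-failure clause, unlike the other long-term endpoints, and the SAP's carry-over sentence does not clearly supply one

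*SAP*

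**What the plan says.** Protocol 7.3.3 defines Single Procedural Success as freedom from documented symptomatic AF, AT or AFL of unknown origin "during the effectiveness evaluation period (Day 91-Day 365) following a single index ablation procedure". The synopsis in protocol section 4 says the same. SAP 7.4.4.3 repeats the definition and adds: "Subjects who had repeat procedure(s) for the study arrhythmia post the index procedure will be deemed failures of this endpoint". SAP 7.11.3 reports the number and percentage of successes, with a Kaplan-Meier analysis of "time to first documented symptomatic atrial arrhythmia (AF, AT or AFL) recurrence following a single index ablation procedure". None of these places mentions acute procedural failure.

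The neighbouring endpoints do mention it:

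- **Secondary 12-month endpoint (SAP 7.4.3):** acute procedural failure "will also be deemed a failure of this endpoint".
- **Symptomatic freedom (SAP 7.4.4.3):** acute failure counts, and is spelled out to include "use of non-study catheter for PV isolation, and failure to have energy delivery with the study device due to ablation system malfunctions".
- **Freedom with additional failure modes (SAP 7.4.4.3):** the first listed mode is "Failure to achieve acute procedural success".

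SAP 7.1.3 decides who is analysed. Under Condition 1, if isolation was completed with commercial RF for a reason related to the study system, the subject is an acute failure and stays in both the acute and the long-term analyses. If the reason was unrelated, the subject is excluded from both. Condition 2, on use of the study system outside the PV/CTI region, ends with: "Subjects who failed the acute effectiveness endpoint will also be considered failures for the long-term effectiveness endpoint".

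**The concern.** A programmer working from SAP 7.4.4.3 would code acute failure as a failure of three long-term endpoints and not of the fourth. The subjects affected are those whose veins the study system could not isolate and for whom another device finished the work. If they then have no symptomatic recurrence and no repeat procedure, they meet the written definition of Single Procedural Success.

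Two things are at stake. A rate reported for the investigational system would include some results obtained with a different device. The endpoints would also stop being coherent: Single Procedural Success is symptomatic freedom with the further demand that no repeat procedure took place, so every success on it should also be a success on symptomatic freedom. Without the acute-failure clause that is no longer so.

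**Working it through.** **1. Failure modes side by side**

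| Endpoint | Arrhythmia, Day 91 to 365 | Acute failure | Repeat ablation |
|---|---|---|---|
| Secondary, 12 months | any documented | failure | not listed |
| Symptomatic freedom | symptomatic | failure | not listed |
| Freedom with additional failure modes | any documented | failure | more than one in blanking, or any afterwards |
| Single Procedural Success | symptomatic | not listed | any for the study arrhythmia |

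**2. One subject traced through.** Isolation is completed with commercial RF because the study system could not achieve it. No symptomatic episode and no repeat procedure follow. SAP 7.1.3 Condition 1 makes the subject an acute failure and keeps the subject in the long-term analyses. Symptomatic freedom: failure. Single Procedural Success, read literally: success.

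**3. Does the analysis text settle it?** No. SAP 7.10 names acute failure as a Kaplan-Meier event for the secondary endpoint. SAP 7.11.3 names only recurrence for Single Procedural Success, but it does the same for the two freedom endpoints, whose definitions do count acute failure. Its silence therefore proves nothing either way.

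**4. The plan's own acute figure.** No figure is planned for Single Procedural Success. The relevant input is the acute endpoint in SAP section 6: 97% anticipated, goal 90%, n = 100, one-sided 0.025, exact binomial, power above 80%. The exact rule requires at least 96 of 100 successes, with attained alpha 0.0237 and power 81.8%. The stated figure is reproduced.

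**5. Size.** Let a be the acute success rate, and s the share of acute failures who otherwise meet the definition.

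Overstatement in percentage points = 100 × (1 − a) × s

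- Expected acute failures at a = 0.97: 0.03 × 135 = 4.05 subjects.
- Probability of at least one: 1 − 0.97^135 = 98.4%.
- Ceiling (s = 1): 3.0 points.
- s = 0.65: 100 × 0.03 × 0.65 = 1.95 points.
- s = 0.80: 100 × 0.03 × 0.80 = 2.4 points.
- Ceiling at a = 0.95: 5.0 points.

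The documents give no value for s; 65% to 80% is an assumed range. As an outer limit, with 135 evaluable subjects the acute test needs 129 successes, so a trial that meets its acute goal has at most 6 acute failures: 6 / 135 = 4.4 points.

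These are upper figures because not every acute failure can become a success here. Subjects discontinued before any study energy was delivered are outside the PP set, and protocol 19.4.2 follows them for only 3 months.

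**The case against.** The best reply is that SAP 7.1.3 already covers this. The section opens as guidance for acute and long-term effectiveness endpoints in the plural, the carry-over sentence carries no limit of its own, and the SAP moves loosely between singular and plural. Single Procedural Success is a Day 91 to 365 effectiveness endpoint, so failing acute failures on it is a natural reading. This has force. A reader might infer that the plan definitely counts acute failures as successes; the documents do not support that. Nor do they settle the opposite. The sentence closes Condition 2, which concerns a different situation. It refers to one long-term endpoint without naming it, and SAP 7.4.3 uses that label for the secondary endpoint. The other endpoints also restate the rule instead of relying on it.

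A second reply is that the endpoint contrasts one procedure with several and was never meant to isolate the device. Acute success and use of non-study devices are reported separately, so little is hidden. If that is the intention, the plan should say so. It would sit awkwardly with Condition 3, which removes subjects ablated with commercial devices outside the PV region precisely to keep non-study device effects out of the long-term results.

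Three further inferences should be resisted:

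- **That this endpoint is easier to pass than symptomatic freedom.** It is stricter on repeat procedures and at most looser on acute failure. Which rate comes out lower depends on how often repeats occur.
- **That the bias is 6.5 to 8 points.** That needs a 90% acute rate (10% × 0.65 to 0.80), which is the null boundary. It implies 13.5 acute failures in 135, more than double the 6 the acute test allows.
- **That any use of a commercial catheter could be credited.** Subjects switched for reasons unrelated to the study system are excluded under Condition 1.

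**Conclusion.** The point holds as an omission and an unresolved ambiguity, not as a demonstrated miscount. Both documents leave acute failure out of Single Procedural Success and include it in the three comparable endpoints, and the only general rule that could fill the gap is unclear in scope. If the literal reading were programmed, the rate would be overstated by at most about 3 percentage points at the planned 97% acute success, and by about 2.0 to 2.4 points under the assumed 65% to 80%. The direction is always favourable to the study system. SAP 7.4.4 and 7.11 make the endpoint descriptive, so no hypothesis test, sample size, power figure or success criterion is affected. It is a minor point, worth settling before the 12-month data are analysed.

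**What to change.** Add to the Single Procedural Success definition in SAP 7.4.4.3 and protocol 7.3.3 (and the matching synopsis entry): *Acute procedural failure, as determined under SAP 7.1.2-7.1.3, is a failure of this endpoint; subjects whose PVI was completed with a commercial device for reasons unrelated to the study system remain excluded.* The second half matters: a clause that failed every use of a non-study device would contradict the Condition 1 exclusion.

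In SAP 7.11.3, count acute failure as an event at Day 0 in the Kaplan-Meier analysis of this endpoint. The same line would help the two freedom endpoints, whose Kaplan-Meier text is also silent. In SAP 7.1.3, move the carry-over sentence out of Condition 2 and state that it applies to all long-term effectiveness endpoints.

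The cost is a few sentences and a slightly less favourable reported rate. No extra data are needed, because acute outcome and use of a non-study catheter are already collected.

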## 7.5 Analysis of Primary Endpoints

The primary safety and effectiveness endpoints will be evaluated based on 3-month follow-up and procedural data respectively. The hypothesis testing of these primary endpoints will be performed once all subjects treated with the STSF catheter and TRUPULSE™ Generator have completed their 3-month follow-up. The results will be reported and considered as final in the 3-Month CSR. And there will be no updates made to the primary endpoints in the Final CSR. The 3-Month CSR will be submitted as a part of the CE mark application dossier.

### **7.5.3 Criteria for Study Success**

Hypothesis testing of the primary safety and primary effectiveness endpoints will be performed when all subjects have completed at least 3 months of follow-up. The analysis results will be reported in a 3-Month CSR. The study will be considered a success if both primary safety and effectiveness success criteria are met based on the 3-month follow-up data.

Regardless the trial success is achieved or not based on the 3-month follow-up data, hypothesis testing of both primary endpoints won't be performed again using the 12-month follow-up data.

## 7.6 Sensitivity Analyses

The sensitivity analyses will be performed for the primary endpoints based on 3-month follow-up data.

### 7.6.1 Primary Safety Endpoint

- **Sensitivity to Analysis Set**

The hypothesis testing will be performed in the SP analysis set for the primary safety endpoint.

- **Best-case Scenario**

The PAE rate will be estimated by treating subjects with missing primary safety outcomes as free from primary safety events in the SP and mITT analysis sets.

- **Worst-case Scenario**

The PAE rate will be estimated by treating subjects with missing primary safety outcomes as failures in the SP and mITT analysis sets.

- **Tipping Point Analysis**

Tipping point analysis will be performed for the primary safety endpoint to assess the impact of missing outcomes on the safety conclusion. The PAE rate will be updated one by one by incrementally treating a subject with a missing outcome as failure to evaluate whether a tipping point is identified. If the upper bound of the exact two-sided 95% confidence interval of a PAE rate is greater than the performance goal of 12%, then the tipping point is considered identified. Otherwise, no tipping point is found. The analysis will be performed in the mITT and SP analysis sets.

